11.3 Content of statistical analysis	
11.4 Statistical analysis of population	
11.5 Statistical analysis method	29
12. Ethical considerations	29
13. Abbreviations	
14. References	
Appendix 1	
Appendix 2	
Appendix 3	

1. Background

Postherpetic neuralgia (PHN) is the most common complication of herpes zoster (HZ) and it is a kind of severe and intractable pain. According to meta-analysis data, the annual incidence of this disease is 3.9-42.0/100,000 people¹. The annual incidence of HZ is 3‰-5‰, about 5%-30% of patients with HZ have PHN, and 30%-50% of PHN patients have experienced persistent pain for more than 1 year², of which middle-aged and elderly people are the main population of PHN. Clinical manifestations of the disease for patients suffering from nerve distribution of sudden or persistent burning, tingling, jumping pain or knife cutting pain, many pain allergies or pain abnormalities, such as wind, light touch can produce severe pain, often affect diet and sleep.

Due to prolonged severe pain, patients often have mental symptoms such as depression and irritability. In the area of skin damage, scars, pigmentation or pigment shedding left after the skin lesion can be seen. Although the occurrence and prognosis of this disease are related to many factors, the body's own immune function status has a direct impact. For patients with strong immunity, even without medicine, they can contain varicellazoster virus through their own strong immunity and heal themselves quickly. For people with low immunity, high work pressure, staying up late, sick, overworked, or older patients with basic systemic diseases, the incidence of PHN is extremely high, and severe cases often have recurring attacks. Even the pain lasts for months or years, which seriously affects the patient's quality of life, and even leads to depression of the patient, seriously affecting their living ability and social activities, and increasing the burden on individuals and society.

For patients with PHN, antiviral and analgesic treatments are often used clinically to regulate immune function and nourish nerves. Because the varicella-zoster virus has considerable nerve and skin toxicity, when the subcutaneous nerves are destroyed by the virus for a long time, although some antiepileptic drugs (such as gabapentin, pregabalin), tricyclic antidepressants (such as nortriptyline), opioids, 5% lidocaine

patch, etc., as well as nerve block therapy can relieve the patient's pain to a certain extent, but may cause serious side effects, and the treatment effect is not good. Pain is prone to recurrence after the drug is stopped, making PHN become a pain problem in the medical field and a potential killer of the health of middle-aged and elderly people. Therefore, finding a treatment method that can effectively relieve the pain of patients with PHN without pharmacological side effects has become the common demand of today's society and the majority of pain patients, and has strong clinical research significance.

According to clinical experience and related literature reports, electroacupuncture has a certain analgesic effect on PHN. According to Chinese National Knowledge Infrastructure (CNKI) literature reports, Therapies such as blood pricking, cupping, ozone, acupoint embedding, moxibustion, acupuncture bloodletting, and fire needling have a certain therapeutic effect on PHN. There is no high-quality clinical randomized controlled study specifically aimed at the analgesic effect of electroacupuncture in the treatment of PHN. A correlation study retrieved in the National Center of Biotechnology Information (NCBI) in the United States reported that the effectiveness of electroacupuncture at Jiaji points combined with moxibustion and intermediate frequency treatment on PHN³, and Tongji Medical College of Huazhong University of Science and Technology reported that electroacupuncture can improve the heat sensitivity and mechanical sensitivity of rats with PHN⁴. However, there is no report on the clinical randomized controlled (RCT) study of the analgesic effect of electroacupuncture on PHN.

In view of the high epidemiological incidence of PHN, the severity and stubbornness of pain, the disease is insensitive to many drugs, and the existence of drug resistance and many drug side effects, to bring great pain and distress to patients, so the treatment of PHN has become a world problem. However, the clinical randomized controlled study related to the analgesic effect of electroacupuncture on PHN has not been reported in the literature so far. Therefore, our research group initiated this clinical trial, mainly on Ashi point, combined with the distal acupoints Zhigou and Yanglingquan, to evaluate whether electroacupuncture can effectively relieve the pain of patients with PHN, and to provide a strong basis for clarifying the treatment of PHN by electroacupuncture.

2. Study Objectives

The objective of this study is to examine the analgesic effect and safety of electroacupuncture and sham electroacupuncture for the treatment of PHN.

3. Methodology

3.1 Trial design

The Analgesic Effect of Electroacupuncture on Postherpetic Neuralgia (AEEPN) study is a multicenter, prospective, parallel-arm, randomized, participant-blinded, sham electroacupuncture-controlled clinical trial of an estimated 448 patients with PHN, which follows the Declaration of Helsinki and the Quality Management Practices for Clinical Trials of Medical Devices. The study duration (as shown in Figure 1) is about 10 weeks, which includes a washout period (7 days or more), a screening observation period (3 to 7 days), a treatment period (4 weeks), and a follow-up period (1 month). AEEPN is conducted at 7 hospitals in China and the ethics committee of each hospital approved the study protocol.

3.2 Randomization

Eligible patients are randomly allocated in a ratio of 1:1 to the EA or SEA group by a central randomization system (Clinical Research Data Collection and Management System of Jiangsu Province Hospital of Chinese Medicine). Multi-center stratified variable block randomization is used, and the block size of each center is randomly set to 4, 6, and 8. Considering that the number of patients in each stratum fluctuates due to block variation, 21 stratums are preset at random and take the first 7 groups with the number of patients equal to 64 as the final grouping. The randomization sequence is

generated and validated by an independent statistician using R software, and then imported into EDC's central randomization system and kept by an administrator who do not participate in this trial. The central randomization system has set strict personnel permissions, and no one has right to view the randomization scheme except the highestlevel system administrator. After participants meet all the inclusion criteria and complete the baseline assessment, an acupuncturist will log in to the central randomization system to apply for random numbers which will be displayed then, and the patients will receive the corresponding treatment. The Clinical Research Coordinators (CRCs) will be responsible for enrolling participants, obtaining informed consent, and CRF recording.

3.3 Blinding

Patients and CRCs (i.e., outcome assessors, data recorders, data entry clerks and statistical analysts) are blinded to the group assignment. Due to the nature of the intervention, acupuncturists are not be blinded to the treatment.

3.4 Sample size

According to previous studies, it is anticipated that a difference in primary outcome (NRS-11) between EA group and SEA group is 1.2 and the combined standard deviation of the two groups is 3.5. To achieve 90% statistical power and control the type I error rate below 0.05, we calculated by PASS 15 that a sample of 448 participants (224 participants in each group) will be required to detect a two-sided significant difference between the two groups and compensate for a dropout rate of 20%. All participants are equally distributed among 7 clinical centers, and 64 participants per center will be recruited.

4. Subjects

4.1 Diagnostic criteria

Guidelines for the management of herpes zoster based on the European consensus Part 1: diagnosis (under the guidance of the European Dermatology Forum (EDF) and the European Academy of Dermatology and Venereology (EADV), 2017)⁵, and the 2016 edition of the guidelines and specifications of the Chinese expert consensus on the diagnosis and treatment of postherpetic neuralgia: have a clear history of acute HZ and the pain persists for more than 90 days after the onset of erythematous macules and rash.

The auxiliary indications for PHN:

- The lesions are usually accompanied by paroxysmal, persistent or evoked pain, sensory abnormalities and hyperalgesia, and have the characteristics of distribution according to innervation area;
- The lesions may be accompanied by manifestations of autonomic nervous dysfunction such as hyperhidrosis;
- Local skin can be seen with residual scars or pigmentation;
- Patient's ability of daily living changes, that may be accompanied by sleep disorders, anxiety, low mood and depression.

4.2 Eligibility criteria

- Meet the diagnostic criteria for PHN;
- Men or women between 45 and 75 years;
- Diagnosed with moderate or higher pain during the screening observation period (daily pain scores of 11-point numeric rating scale (NRS-11) were collected during the observation period, and the average pain score ≥4);
- Did not participate in other ongoing clinical studies;
- Volunteer to participate in the AEEPN trial and sign the informed consent form

(ICF).

4.3 Exclusion criteria

- patients who are currently receiving, or have received more than one "permitted concomitant medications" or any "prohibited concomitant medications and treatments" for the treatment of PHN at least 14 days before the screening observation period, and are unwilling to undergo a washout period (≥7 days), or patients with serious safety issues during the washout period or observation period;
- Patients who are expected to receive any new prescription drug or other treatment for PHN after the start of the trial;
- Patients with serious uncontrolled medical conditions, such as cardiovascular, lung, liver, kidney, gastrointestinal tract, metabolism, endocrine, nervous system, respiratory system, urogenital system and other serious diseases, or systemic organ dysfunction, malignant tumor, hematologic disease such as bleeding tendency or coagulation dysfunction, serious mental illness such as depression or schizophrenia Symptoms, hepatitis B antigen or hepatitis C antibody positive known state or history of immune dysfunction, history of HIV infection, etc.;
- Patients with severe pain unrelated to PHN, such as after surgery for clinical major diseases;
- Patients with PHN who have received nerve intervention or other neurosurgical treatment, such as selective nerve damage, percutaneous radiofrequency thermocoagulation or pulsed nerve modulation technology, etc.;
- Patients with some special types of herpes zoster, such as those with meninges, cornea, conjunctiva, ear involvement, visceral herpes zoster, generalized herpes zoster;
- Patients with skin ulceration, new herpes, or skin infection;
- Patients with cardiac pacemaker, metal allergy or severe fear of needle;
- Patients who are unable to give full informed consent or cannot cooperate with pain

scale assessment due to mental, mental, linguistic or behavioral disorders;

- Patients who have poor compliance or are prone to fall off due to other reasons, such as the current residence is not in the city where the recruitment hospital is located, or the working environment changes frequently;
- Pregnant and lactating women

4.4 Subject termination

- Those who cannot tolerate acupuncture, have serious adverse events during the treatment, and should stop the clinical trial of this case according to the doctor's judgment;
- During the research period, the subject has serious complications or other serious diseases and needs emergency measures; or has other diseases that affect the observation of the test, and the clinical trial should be stopped according to the doctor's judgment;
- During the clinical trial, the subject is unwilling to continue the clinical trial for various reasons, and actively asks the doctor in charge to withdraw from the clinical trial.

4.5 Subject dropping and handling

Criteria for Subject dropping: subjects who have received informed consent and screened qualified to enter the randomized trial, who fail to complete the course of treatment and observation period specified in this program for some reason, are regarded as dropped cases.

Disposal of subjects dropping:

• When the subject falls off, the person in charge of the project will contact the subject as much as possible, ask the reason, record the details, and complete the evaluation project as much as possible by means of door-to-door visits, follow-up appointments, telephone calls, and WeChat.

- If the test case is withdrawn due to needle allergy or fainting or other adverse reactions, and treatment is ineffective, the person in charge of the project will take corresponding measures based on the actual conditions of the subjects.
- Relevant test data are properly kept for the dropped cases and kept in files for subsequent statistics of the full analysis set. There is no need to re-recruit subjects to fill the number of dropped cases.

4.6 Subject elimination

- Due to the patient's concealment of the condition or other conditions, cases that did not meet the inclusion criteria and met the exclusion criteria were found after inclusion.
- After being included, they refused to participate in the trial and have not yet recorded any clinical data.

Before the statistical analysis of the data, the statistician and the main researcher shall discuss and judge whether the case should be eliminated.

5. Interventions

5.1 Lifestyle education

All participants will receive lifestyle interventions as basic treatment: advocate reasonable diet for patients, promote healthy diet knowledge of low-salt, low-fat and low-sugar; identify patients' concerns, help patients relieve stress factors and reduce avoidance behavior, establish a positive doctor-patient relationship; review patients' drug dosage, quality of life, daily activity ability, anxiety and depression assessments, provide healthy lifestyle education.

Electroacupuncture therapy program is developed by the consensus reached by acupuncture experts based on previous studies of electroacupuncture for PHN. This study will use Hwato brand disposable acupuncture needles (size: 0.30×40 mm), placebo blunt needles (size: 0.40×13 mm), insulating adhesive pads (Chinese patent

number: ZL 2020 2 1980069.2), and SDZ-V electroacupuncture apparatuses.

5.2 Electroacupuncture (EA) group

Points selection: ipsilateral Zhigou (SJ6), Yanglingquan (GB34), and Ashi points.Location: Refer to the National Standard of the People's Republic of China "Acupoint Name and Location" (GB/T 12346-2006) for acupoint location.

Operation method: Participants take the appropriate position on the treatment bed according to the location of PHN. After routine skin disinfection, the sterile insulating adhesive pads are placed on ipsilateral Zhigou, Yanglingquan and Ashi points. Then acupuncture needles are inserted vertically into the skin of Zhigou and Yanglingquan through the pads approximately 15 to 20 mm, and performs slight, equal manipulations of twirling and lifting to reach the sensation of deqi (known as soreness, numbness, distention, heaviness or other sensations, which is considered to indicate effective acupuncture). Besides, acupuncture needles are inserted obliquely (at an angle of 30 to 45 degrees) into the skin of Ashi points through the pads approximately 10 mm, and point the needle towards the painful area of PHN. The paired poles of electroacupuncture apparatus are connected to the needle handles at ipsilateral Zhigou and Yanglingquan, and for Ashi points, the paired poles are connected to the head and tail acupoints of the long axis of the painful area. The waveform of electroacupuncture stimulation is a continuous wave with a frequency of 2 Hz and a current intensity of 1-5 mA (causing mild tremor of the skin around the acupoints without pain), and continue the electroacupuncture treatment for 30 minutes.

Frequency and duration of treatment: All patients will receive electroacupuncture treatment once per day, 5 times a week for 4 consecutive weeks (20 treatments in total).

5.3 Sham electroacupuncture (SEA) group

Participants randomly assigned to the SEA group will received sham electroacupuncture by using placebo blunt needles at the same acupoints. After

disinfecting the skin and placing the sterile insulating adhesive pads on ipsilateral Zhigou, Yanglingquan and Ashi points, placebo blunt needles are inserted through the pads and reach the insulating adhesive layer, causing the participants to feel the needle resistance (a sensation of needle insertion). Other procedures, electrode placements, parameter of electroacupuncture apparatus and treatment settings are the same as in the EA group, but with no skin penetration or electricity output.

6. Concomitant Medications

6.1 Permitted concomitant medications

During the first visit, the medication usage of the participants in the last 2 weeks will be inquired in detail and recorded, including drug name (or other therapy name), indications, dosage unit, frequency of administration, route of administration, and start and end time of medication.

Participants will be allowed to take only one of the following medications to treat PHN if they take a stable dose level for PHN at least 14 days before the screening period:

- any anticonvulsant drugs (e.g., pregabalin, gabapentin, oxcarbazepine, carbamazepine);
- any one of serotonin-norepinephrine reuptake inhibitors (SNRIs) (venlafaxine, duloxetine, milnacipran);
- any TCAs (e.g., amitriptyline, nortriptyline, clomipramine, doxepin, desipramine);
- any opioid analgesics (e.g., tramadol, codeine, morphine, oxycodone, methadone);
- any one of oral Non-steroidal anti-inflammatory drugs (NSAIDs) (e.g., ibuprofen, aceclofenac, celecoxib, nimesulide, meloxicam, diclofenac, ketotifen, naproxen).

Afterwards, the participants should maintain the medication regimen during the entire study period unless there are safety issues during the observation period. If the participant wants to adjust the medication regimen, he or she can apply to his or her doctor, who can adjust the medication plan after the specific condition has been

assessed.

Participants will be allowed to take a stable dose of the following drugs for the treatment of underlying diseases throughout the study:

- benzodiazepines, non-benzodiazepines (e.g., eszopiclone) or related drugs for insomnia;
- stable dose of diuretics, calcium antagonists or related drugs for the treatment of hypertension;
- the selected 5-serotonin reuptake inhibitor for depression (e.g., sertraline, fluoxetine);
- β agonists or anticholinergic drugs for chronic obstructive pulmonary disease;
- oral aspirin for cardioprotection;
- hypolipidemic drugs;
- vitamin D, calcium supplements, or related drugs for the prevention of osteoporosis;
- other drugs not included above and not related to the treatment of PHN.

6.2 Prohibited concomitant medications

The prohibited concomitant medications for the AEEPN trial are as follows:

- any topical medication for PHN, including 5% lidocaine patch, lidocaine ointment, capsaicin patch, NSAIDs and any other topical drug preparations for the treatment of PHN;
- monoamine oxidase inhibitors or any other antidepressants not included in the permitted concomitant medications;
- steroids;
- mexiletine;
- lamotrigine;
- ibuprofen and codeine phosphate tablets;
- alpha-lipoic acid;
- evening primrose oil;

- any skeletal muscle relaxant (e.g., botulinum toxin, baclofen);
- any antipsychotics or neuroleptic medications;
- any other medication for pain relief not included above.
- during the study period, any neuromodulation techniques (e.g., nerve pulse radiofrequency, nerve electrical stimulation), nerve block, and other forms of analgesic therapy that may confuse the evaluation of PHN is prohibited.

6.3 Rescue medication

Participants will be allowed to take oral paracetamol/acetaminophen (up to 2 grams per day, as needed) as rescue medication for unacceptable pain. The use of rescue medication must be promptly recorded in the CRF and entered into the EDC system, and all participants are discouraged from receiving any prohibited medications or treatments throughout the trial, if received, they are asked to document all.

7. Outcomes measures

7.1 General record items

Hospital code, case random number, abbreviation of subject's name, start date of trial.

7.2.1 Biological information

Demographic characteristics: gender, age, height, weight, medical history, marriage, education

History of PHN: course of disease, location of onset, TCM syndrome, medication and treatment for PHN in the past 14 days

Basic diseases: medication and treatment for basic diseases in the past 14 days **Observation time point**: Collect the above data before enrollment

7.2.2 Outcomes

7.2.2.1 primary outcome

11-point numeric rating scale (NRS-11)⁶⁻⁸: Use a scale of 0-10 to represent different degrees of pain: 0 means no pain; 10 means severe pain.

The grading standard of pain degree is: 0: no pain; 1-3: mild pain; 4-6: moderate pain; 7-10: severe pain.

Time Frame: Change from Baseline at 4 weeks

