7.2.2.2.2 Visual analogue scale (VAS)^{8,9}

A horizontal line 10cm long (or 100mm), one end of the horizontal line indicates no pain (0); the other end indicates the most severe pain imaginable (10); the middle part indicates different degrees of pain. Ask the subjects to draw a vertical line mark at the place closest to their pain level to quantify the intensity of their pain.

no pain worst imaginable pain

Time Frame: Change from Baseline at 1 day, 3 days, 1 week, 2 weeks, 3 weeks and 4 weeks, one-month follow-up after treatment

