7.2.2.2.6 Average number of pain episodes (ANPE)¹⁶ (Within 24 hours)

- Painless: 0 times
- Intermittent pain: 1-50 times (optional 1-2, 3-5, 6-10, 11-50)
- Persistent pain: >50 times

Time Frame: Change from Baseline at 1 day, 3 days, 1 week, 2 weeks, 3 weeks and 4 weeks, one-month follow-up after treatment

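### Primary NRS-11: the label at 10 does not set it apart from 7-9, and the baseline for the change score is undefined, with conflicting timing

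*Protocol*

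**What the plan says.** **Scale.** Section 7.2.2.1 defines the primary outcome: "Use a scale of 0-10 to represent different degrees of pain: 0 means no pain; 10 means severe pain". It then gives the bands: "0: no pain; 1-3: mild pain; 4-6: moderate pain; 7-10: severe pain". For the VAS, section 7.2.2.2.2 says that "the other end indicates the most severe pain imaginable (10"). Both scales are rated at day 1, day 3, weeks 1 to 4 and the one-month follow-up.

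**Endpoint.** The primary outcome carries one further line: "Time Frame: Change from Baseline at 4 weeks". Neither this section nor any other says which reading or readings make up baseline.

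**Scores collected before treatment.** Section 3.1 gives a screening observation period of 3 to 7 days. Under section 4.2, "daily pain scores of 11-point numeric rating scale (NRS-11) were collected during the observation period", and their average must be at least 4 for entry.

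**Timing of baseline.** Section 3.2 has the baseline assessment completed before the acupuncturist requests the random number. The recruitment sequence in section 12 lists baseline evaluation after random grouping.

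**Pain type and recall.** For NRS-11 the protocol does not say whether current, average or worst pain is rated, or over what period. The number of pain episodes does have a window ("Within 24 hours"), and the ZBPI in Appendix 2 lists worst, least, average and current pain as separate items.

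**The concern.** The label at 10 is the label of the whole 7-10 band, so it gives a patient or assessor no reason to separate 10 from 7, 8 or 9. The VAS text shows that the authors had a stronger anchor in mind for a pain scale. Entry requires a mean of 4 or more with no upper limit, so patients with severe pain are enrolled. If some of them score 10 for pain that is severe but not extreme, worsening cannot be recorded and differences at the top are compressed. A SAP cannot repair a label once patients have answered to it.

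The baseline is half of a change score. If it is one reading, its day-to-day noise enters the primary variable in full under the methods named in section 11.5. For quantitative data these are t and Wilcoxon tests, with no baseline-adjusted model. Several daily scores are already in hand and could reduce that noise at no cost. A baseline taken after allocation would also be a weaker reference than one completed before it, because the acupuncturist knows the group from the moment the random number is shown. The protocol supports both orders.

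**Working it through.** **1. The anchors side by side**

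| Item | Where | Meaning of the top |
|---|---|---|
| NRS-11, point 10 | 7.2.2.1 | severe |
| NRS-11, points 7 to 10 | 7.2.2.1 | severe ("7-10: severe pain") |
| VAS, point 10 | 7.2.2.2.2 | most severe imaginable |

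A score of 10 lies inside the severe band, so the two NRS-11 lines can both be true. The defect is that the end label carries no information beyond the band label, and that two pain scales used at the same visits have different tops.

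**2. The timing of baseline**

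- Section 3.2: inclusion criteria met, then baseline assessment, then random number, then treatment.
- Section 12: consent, then random grouping, then baseline evaluation, then intervention.

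The two orders cannot both hold.

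**3. The planned sample size**

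Inputs from section 3.4: difference 1.2, SD 3.5, two-sided alpha 0.05, power 90%, dropout 20%.

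- n per arm = 2 × [(1.960 + 1.282) × 3.5 / 1.2]² = 178.8, rounded up to 179.
- With dropout: 179 / 0.8 = 223.75, rounded up to 224 per arm, 448 in total.

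This matches the protocol. Power at 179 evaluable per arm is 90.0% by the normal approximation and 89.9% by the noncentral t.

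**4. What an averaged baseline could be worth**

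The documents give no day-to-day SD, so this step rests on four assumptions:

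- baseline is now a single reading;
- 3.5 is the SD of the change score (section 3.4 does not say whether it refers to change or to score);
- daily errors are independent;
- the within-patient day-to-day SD, s, is 1 to 2 points. That makes s² between 1/12.25 = 8% and 4/12.25 = 33% of the change variance.

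Replacing one baseline reading by the mean of k readings replaces s² by s²/k, so Var(change) = 3.5² − s²(1 − 1/k) = 12.25 − s²(1 − 1/k). The week-4 reading is left as it is.

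| s | k | Variance | SD | 12.25 / variance | Power at 179 per arm (noncentral t) |
|---|---|---|---|---|---|
| 1 | 3 | 11.58 | 3.40 | 1.06 | 91.4% |
| 1 | 7 | 11.39 | 3.38 | 1.08 | 91.8% |
| 2 | 3 | 9.58 | 3.10 | 1.28 | 95.5% |
| 2 | 7 | 8.82 | 2.97 | 1.39 | 96.8% |

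The ratio in the fifth column is the equivalent increase in sample size, 6% to 39%. If baseline is already the mean of the daily scores, the gain is zero.

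**The case against.** The strongest reply is that most of this is wording. A 10 is severe pain, so nothing in section 7.2.2.1 is false. The text describes the scale and is not the patient-facing item, which is not in the document. Sections 9.1 and 9.2 provide for operating procedures and assessor training, where the exact question could sit. How baseline is derived from several scores is routine SAP content, and the SAP is not at hand. The trial also reaches its planned power on its own inputs.

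Much of this stands, and it rules out four stronger readings that a reader might infer:

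- **That the anchor contradicts the grading.** It does not. It fails to distinguish the top point.
- **That a ceiling exists.** No baseline distribution is given, and nothing says what patients are shown. A loss of sensitivity at the top is possible, not demonstrated.
- **That the plan discards the daily scores, or that the endpoint uses one momentary reading.** The text says neither. Section 3.2 does name a baseline assessment separately from meeting the inclusion criteria, which makes a separate reading plausible but does not establish it. Since the type of pain is unspecified, it cannot be assumed to be current pain.
- **That precision is known to be lost.** The gain depends on all four assumptions above. A baseline-adjusted analysis, which a SAP could specify, would also lessen the effect of a noisy baseline.

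The objection does not remove two points. The scale definition in the protocol is weak at its top end and differs from the VAS, and a SAP cannot mend that after data collection. The order of baseline and randomization is a conflict within the document, not an omission. The missing recall period, taken alone, is only missing detail and is treated here as a clarification.

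**Conclusion.** The point holds in limited form. The primary scale's top anchor is poorly distinguished from the 7-9 scores and inconsistent with the VAS, and it may cost sensitivity in patients with severe pain. The size of that cost cannot be derived from the documents. Baseline is undefined even though suitable daily scores are collected, and sections 3.2 and 12 disagree on whether it precedes randomization.

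The precision at stake ranges from nothing, if baseline is already the mean, to a fall in SD from 3.5 to between 3.40 and 2.97. The second case takes power at 179 per arm from about 90% to 91-97% and requires a single-reading baseline, independent daily errors, a day-to-day SD of 1 to 2 points and 3.5 as the SD of change. These figures concern the baseline only and do not measure the effect of the anchor or the recall period. The planned 448 is correct on its stated inputs. This is an inexpensive improvement to the primary measurement and does not show that the trial is underpowered.

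**What to change.** 1. In section 7.2.2.1, anchor 10 as the worst pain imaginable, in line with the VAS, and keep 7-10 as the severe band.
2. Define baseline for the primary change score as the mean of the daily NRS-11 scores from the screening observation period, all taken before randomization.
3. Reconcile sections 3.2 and 12 so that both place the baseline assessment before randomization, as this definition requires.
4. As a clarification, state one pain type and recall period for NRS-11 at every visit, including the daily screening scores. Average pain over the last 24 hours is one option, and it suits the day-1 and day-3 ratings.

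The cost is a few lines of protocol text and the wording of one CRF item. The daily scores are already collected, so no visit, assessment or patient is added and the sample size need not change. The anchor and the question should be settled before patients are rated. If some have already been rated, record the date of the change, because scores before and after it may not be comparable.
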